## **Observation Tool**

### **Observation of delivery of HIVST (ANC/ART)**

1. Please describe the location where the ANC/ART is located. Please note the layout of the buildings, patient flow. Please take note of people present (*men or women; average age; children; health; economic status*) etc.; is the clinic integrated or are services offered separately; Are there any distinguishing features or services that make people to be identified? What other distinguishing features of interest to HIVST are there? In your opinion is there any feature that might influence HIVST decisions?
2. Please describe how the test kits are given out to clients. Please describe how the test kits are distributed. Is it done in the open or in a confidential space; how free are clients to come and collect the test kits; what kind of information is given out concerning usage of the kits; what time are kits given out (what time do people come to collect?), what gender and age of clients come to collect the test kits; is adequate information given; what is the immediate reaction from the client when given the kit?
3. Clients are asked to go and give the test kits to another person at their home. Do people accept to collect these kits? Are there men that collect test kits for their partners? How easy is it for women to collect test kits for their partners? How do the health staff explain this? Do clients ask any questions and if so, what kind of questions did they ask in relation to secondary distribution? How free are women to collect the test kits for their male partners? What questions did the clients have concerning the HIVST process? Did the health care workers discuss any potential social harms with the client, so what was the response from the clients?
4. When offered the test kit, were there any clients that wanted to test at the facility? Where did the client test from?
5. If the client tested from the ANC/ART Clinic, what assistance did the client ask for regarding use of the HIVST kit? Were there any other questions asked by the client regarding the use of the KIT? Probes, Pre-test counselling (demonstration on how to use, help with reading IFU) post-test counselling (Information on linkage to care in case of a positive result, social harms)
6. Is there anything else you would to add

**Observation checklist for secondary distribution (ANC/ART)**

Characteristics/ features to observe		
1	Location of the distribution point at the clinic	
2	Distinguishing features of the distribution points in relation to other points within the clinic	
3	Process of HIVST kit distribution	
4	Characteristics of individuals collecting HIVST kits	
5	Communication between distributor and individuals collecting the kits	
6	Points of discussion/ communication (if were able to hear any) between distributors and individuals collecting the kits	
7	Testing location (places people prefer to use to conduct HIVST within the clinic)	
8	Assistance self – testers request and why	
9	Complaints/ good things self-testers say about the location	
10	Complaints/ good things self-testers say about HIVST process at the clinic	

Observation tool

Observation of workplace distribution model

1. Please describe the work place. (probes: type of organization, location, social economic class of employees, residential place where employees come from, age groups and gender of employees) In your opinion is there any feature that might influence HIV testing decisions? Is the room providing the HIV service stigma free?
2. Please describe how the HIV test kits are distributed? (what kind of information is given if any, who distributes, at what time, what is the reaction of the client, was adequate information given)
3. How is the quality of counselling provided by the distributor? Use of space. (Privacy/confidentiality, use of flipchart, demonstration of how use of the test kit etc.).
4. What reason did the client give for collection of the kit (probe: convenience, stigma, dislike for finger prick, health service problems e.g. long queues, congestion, stigma) what gender and age come to collect the HIV self - test kit?
5. When offered the test kit, where did the client test from?
6. If the client tested from the work place, what help did the client ask for regarding use of the HIV self-test kit? What kind of assistance did the client ask for (Probe: Pre – test counselling (demonstration, help with reading IFU) Post- test (Information on linkage to care in case of a positive result)
7. What did the distributor do to encourage linkage?
8. Did the client have any questions concerning the testing
9. Is there anything else you would like to add

## **Observation Tool**

### **Observation of delivery of HIVST Community led models (hubs, kantemba, and shops)**

7. Please describe the location where the community hub (shop, kantemba) is located. Please note the layout of the buildings, and flow/ movements of clients. Please take note of people present (*men or women; average age; children; health; economic status*) etc. Are there any distinguishing features or services that make people to be identified? What other distinguishing features of interest to HIVST are there? In your opinion is there any feature that might influence HIV-self testing decisions?
8. Please describe how the test kits are given out to clients. Please describe how the test kits are distributed by the community distributor (shop owner etc)? Is it done in the open or in a confidential space; how free are clients to come and collect the test kits from the community hubs; what kind of information is given out concerning usage of the kits; what time are kits given out (what time do people come to collect?);, what gender and age of clients come to collect the test kits; is adequate information given; what is the reaction from the client when given the kit?
9. When offered the test kit, were there any clients that wanted to test right at the hubs, shops?? Where did the client test from?
10. If the client tested from the hub, kantemba, shop? What help did the client ask for regarding use of the HIV self-test kit? Did the client get the help? Probes, Pre-test counselling (demonstration on how to use, help with reading IFU) post-test counselling (Information on linkage to care in case of a positive result, social harms)
11. Were there any other questions asked by the client regarding the use of the KIT?
12. Is there anything else you would like to add

**Observation checklist for community led**

	Characteristics/ features to observe	
1	Location of the distribution point within the community	
2	Distinguishing features of the distribution point in relation to other points/ places within the community	
3	Characteristics of individuals distributing the test kits	
4	Characteristics of individuals collecting HIVST kits	
5	Process of HIVST kit distribution	
6	Roles played by the distributor (recordkeeping, information giving, demonstration, counselling and education, facilitating linkage)	
7	Communication between distributor and individuals collecting the kits	
8	Availability of records (type of records kept)	
9	Availability of testing room/ space	
10	Disposal of waste	
11	Stocks	
12	Use of aids in communication	
13	Points of discussion/ communication (if were able to hear any) between distributors and individuals collecting the kits	
14	Assistance self –testers request and why	
15	Complaints/ good things self-testers say about the location	
16	Complaints/ good things self-testers say about HIVST process at the community point	

## **Mapping Tool**

### **Group Discussion Guide (NHC)**

Time: 1 hours maximum

1 exercises

Community mapping

Participants:

8-12 members of the Health Committee, mix of men and women

Venue

Community venue that offers privacy (free of distractions). These activities could be conducted in the health centre.

Seating arrangements:

if possible arrange chairs in a semi-circle, without tables.

Materials:

Flipchart

Marker Pens

Scissors/Razor blade

Sticky stuff

Facilitator Notebook

Pencils

Consent forms

Information sheets

AAA size batteries

Digital recorder

A4 envelopes

Preparations:

General

- Drinks and snacks for the participants and facilitators.
- Table of participant details pre-drawn on A4 paper to save time.
- Cards with natural numbers on them to use as identity during discussion i.e. as 1,2,3,4,5,6,7,8,9.

Mapping

- Cards written with different places: bar, shops, tuntembas, clinic, church, guest house, bus station, salons
- Some blank cards
- 2 Flipcharts taped together.

Procedures:

#### Participant characteristics

As you wait for participants to arrive, one facilitator should go around the circle, and, for each participant, record the following: Participant number, Age, Sex, and Marital Status, number of children, source of income, church, and length of time resident in site.

Please note this should be done by the facilitator, not filled in by participants themselves. This should be done before the introduction, with the exception of latecomers.

#### Introduction [15 minutes]

We have selected all of you to represent your community here as we really value what you as the Neighbourhood Health Committee can share with us about your experiences of living in this community. Although we will not be providing money, we will be providing a drink and a snack during the discussion.

#### ADMINISTER INFORMATION SHEET AND INFORMED CONSENT

##### [EXPLAIN THE FOLLOWING]

Ask: Which language are you most comfortable using?

- This will be a 1 hour activity.
- We want it to be as participatory as possible. We want to hear your views. There are no right or wrong answers.
- Please feel free to give your ideas and also give a chance to everyone to speak.
- You may have different ideas from others – that's okay – we want to hear them.
- Any question you feel uncomfortable about, please feel free not to answer it.
- Your names will be kept confidential – when we write up the discussion, we never use people's real names.
- We will be happy to answer any questions you have at the end of the discussion
- Please put your cell phones on silent if possible

- Is it ok with you if we start the discussion?

NOTE: RECORD THE TIME ACTIVITY STARTS

### **Community Resource mapping (45 minutes)**

1. Stick the big flipchart on the wall, or place on a table or floor so that everyone can stand around it.
2. Explain that you would like the group to make a map of the community. It does not have to be accurate, but it needs to show some of the main features and places that people go to.
3. Start with the 'Clinic' card and ask someone to put it on the map. Lay out all the other cards- including the blank cards and hand out markers and sticky stuff. Ask the group to now stick the cards to show where the places are. They can write or draw new cards for other places, or draw directly on to the map.
4. Ask if anyone can draw in some key roads or rivers or other key features.
5. Ask if they can show the entry and exit points- where people *come into* the community and where they *go out?*

Leave the group to build their map by adding any other key features that are found in the community - allow at least 15 minutes for this.

6. Now explain that you will be doing a walk around the community tomorrow. The focus of your research is on HIV self-testing which is being delivered in people's homes by CHIPs.
  - I. -Ask - What are some of the key places or features that may have an influence on or affect the uptake of HIVST that you think are important for us to see on the walk? *Probe for reasons why these places or features have been identified*
  - II. -Ask- We also want to know where people buy their medicines, where people go for their HIV testing; where the counselling services are available? etc.
  - III. -Ask- -We also want you to tell us about the social, cultural and physical differences that exist in your community? *Probe about any differences between zones from a social, cultural and economic perspective that may have an influence of HIVST-i.e. What is it that is in this zone which is not in the other zones? Give details as to what kind of houses are there, what people do in the different zones to earn a living, do they work within or outside the community, the different social economic classes that are found in the different zones, where and who do people interact with either in groups or individuals, what trading spaces, recreational spaces, other organisations or facilities and other testing services are there.,*
  - IV. -On the structure of the clinic, ask about its building structure, location of the VCT clinic and anything else that goes on at the clinic or is found at the clinic that may have an influence or effect on the uptake (or acceptability) of HIVST.
  - V. -Self-testing is not being implemented in all zones, do you think this will affect how community members respond when they see that their friends are not being offered the service (those in control zone)?
7. Ask participants to mark them on the map and find out why they have been identified. Refer to the transect walk observation checklist below [Stress the places that could be linked to HIV self-testing)

Check if there are any other additions from the group about what they think the researchers should know about the community. Thank the participants.

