## 4. Methods

### 4.1 Study population and location

The study population will include individuals aged 16 years or older (the age of consent for HIV testing in Zambia), who access health facility services where HIVST kits are being distributed. The study location is five peri-urban communities in Lusaka, Zambia. These communities vary in population size from 41,825 to 106,000 individuals. In each of the communities, the facility-led model will be implemented in the public health facility and the community-led model will be implemented in all facility catchment areas. Facility-level distribution will utilize the existing systems of service delivery. Distribution of HIVST will be done within the facility and during outreach programs. The VMMC model will target potential VMMC clients within the communities surrounding the clinic during facility-led outreach activities.

The selection criteria of the communities included having a health facility that offers HIV ST services, presence of an ART clinic and a catchment population size of more >40,000. (Figure 1).

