### **Community Participatory Assessments**

This stage will primarily focus on mapping stakeholders and potential distribution points in the community using purposely selected community members. Information collected will also be used to review case studies:

1. Use of Participatory Rapid Appraisal (PRA) tools to elicit community views about 1) potential stakeholders 2) possible HIVST distribution points 3) possible implementation mechanisms for distribution models proposed by the study
2. Tools to be used will include physical maps and social maps – the former for places and key features of the community and the latter for key stakeholders
  - a. Map key stakeholders
  - b. Map potential distribution places
  - c. Identify physical features that will facilitate and or hinder 1) distribution of HIVST kits 2) uptake of HIVST 3) linkage to confirmatory testing 4) linkage to care by those who self-test positive.

- d. Identify social features that will facilitate and or hinder 1) distribution of HIVST kits 2) uptake of HIVST 3) linkage to confirmatory testing 4) linkage to care by those who self-test positive.
- e. Identify social and physical features that will facilitate or hinder implementation of secondary distribution models (ANC and HIV+ individuals)

The mapping exercise will be conducted shortly before the commencement of the study to map potential HIVST stakeholders and HIVST distribution models/points. Selected representatives of the community (opinion leaders) will draw community maps and include features of the community that relate to or may impact positively or negatively on HIVST distribution. The exercise will be facilitated in such a way as to enable the community representatives to reflect/relate the features to the distribution models that the study will explore.

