## **IDI (community led models)**

Thank you for taking time to speak with me today. My name is \_\_\_\_\_ and I am working with Zambart a research organization. In order to increase the uptake of HIV services, HIV self – testing kits are being distributed at the ARTs clinic and ANC. We would like to hear what you think about this as well as what the community thinks. We will record the interview in order to make sure that we capture all of the valuable information that you share with me. We will also be taking down notes so that I do not forget what we have discussed. Please feel free to give honest answers as what we say is confidential. We will not record your name on the tape or on the notes that will be written and no one else will see the tape or the notes besides people who are working on this research project.

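### The neighbourhood health committee mapping script describes home delivery by CHiPs and a control zone, neither of which exists in this study

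*Protocol*

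**What the plan says.** **Mapping script (Appendix 4, Community Resource mapping, item 6).** The facilitator announces a walk around the community and explains: "The focus of your research is on HIV self-testing which is being delivered in people's homes by CHIPs". Five prompts follow. The fifth reads "Self-testing is not being implemented in all zones, do you think this will affect how community members respond" and continues "when they see that their friends are not being offered the service (those in control zone".

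**Study design.** Section 1.5 calls the study observational and says it evaluates five models. Table 1 lists them: VMMC, combined facility- and community-led, workplace, secondary distribution through ANC, and secondary distribution through people who know they are HIV-positive. On coverage, section 4.1 says "the community-led model will be implemented in all facility catchment areas".

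**Purpose of mapping.** Section 4.2, Community Participatory Assessments, says that the exercise is to be run so as to "enable the community representatives to reflect/relate the features to the distribution models that the study will explore".

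**A second guide.** Appendix 4 holds two interview guides for community-led models. The one titled IDI (community led models) opens by saying that "testing kits are being distributed at the ARTs clinic and ANC", and then asks about the kantemba or hub as the distribution point.

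**The concern.** A facilitator using the mapping guide as written would describe to local partners a delivery method that the study does not use, and ask them to comment on a comparison that does not exist. Three things are at stake.

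- Answers on what helps or hinders uptake come straight after the home-delivery statement, so some may concern household visits and not clinics, shops, workplaces or partner delivery. These data serve objective 3.
- The zone prompt can yield only opinions about a control area. Nothing in the study can use them.
- The audience matters. Under section 5.1 neighbourhood health committees are consulted on the selection of some discussion participants, and under section 10.2 their members are trained on social harms and give feedback. They should not be told something untrue about who is offered the service.

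**Working it through.** No figure in the plan depends on this, so the check sets the texts side by side.

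**1. Is home delivery by CHiPs one of the models?**
- Table 1 and Appendix 1 describe five models, and none is home delivery by CHiPs: 0 of 5.
- Section 3 has CHiPs among those trained to offer kits, including for secondary distribution. Appendix 1 has them supporting kantembas, capturing data and tracking linkage at the sites managed by Zambart. Their role is thus wider than kantemba support, but no passage sends them to homes with kits.
- The only distributors described as meeting clients at home are the VMMC promoters (Appendix 1, model 1), who are not CHiPs.

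**2. Is there a control zone?**
- No section defines one.
- The only comparator is facility-based finger-prick testing, in the economic evaluation (sections 4.4.1 and 4.4.3). It is a standard of care, not an area.
- Partial coverage by zone has some basis: Appendix 1 places VMMC visits in designated zones, and the full-coverage statement in section 4.1 is made for the community-led model. So the first half of the fifth prompt may be true of one model. The words "those in control zone" fit none.

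**3. Does the script do what section 4.2 asks?**
- Item 6 is the script's only description of how kits are delivered, and it names a method outside the five. To that extent it contradicts section 4.2.

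**4. How far can the error travel?**
- Items 1 to 5, in which the group builds its map, come before the wrong sentence. The pre-written cards include shops, tuntembas and the clinic.
- Prompts I to IV are generic: places affecting uptake, where people test and buy medicines, differences between zones, and the clinic. Only V refers to a control zone, so 1 of 5 prompts is wrong in itself.
- Item 7 then marks the places named under item 6 on the map, and the Transect Walk Guide uses the map drawn by the committee. The framing can therefore reach the map and the walk.

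**5. How many people?**
- The guide sets 8 to 12 members per group. The number of groups is not stated. Assuming one group in each of the five communities, 5 × 8 = 40 to 5 × 12 = 60 people would hear the script.

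**6. The second interview guide.**
- Its introduction describes a channel that does belong to this study (models 4 and 5), but it heads a guide about kantembas.
- The guide titled IDI for community led models carries the right introduction, and its questions are essentially the same. This is a mismatch of introduction and questions, not a foreign intervention.

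**The case against.** The strongest reply is that this is a slip in one appendix tool with little reach. Objective 3 also rests on focus groups, in-depth interviews, consultations, observations and stakeholder discussions, and most of those guides name the right channels. Within the mapping tool, most of the map is drawn before the wrong sentence is read, four of five prompts are neutral, and no prompt asks about household visits. Committee members should also have heard a correct account: section 4.2 has entry meetings with the Neighbourhood Health Committees, and the script itself calls for an information sheet first. Finally, Table 1 lets communities decide how community-led kits are given out.

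Most of this stands and limits the effect. It does not remove the contradiction. A correct earlier briefing means only that the script conflicts with it, and community choice over distribution does not create a CHiP home-delivery model or a control zone.

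A reader might infer more than the documents support:

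- *That the contextual data as a whole will describe another intervention and comparator.* They will not. Only the mapping and the transect walk are exposed, and even there the framing may distort answers without determining them.
- *That the script ignores clinics and shops.* It elicits them through the cards and prompt IV, though not as distribution models.
- *That mapping comes first, so everything later inherits the error.* The opening of section 4.2 lists mapping after consultations, stakeholder discussion, interviews and focus groups, while Community Participatory Assessments puts it just before the study starts. Stakeholders also have their own meeting and analysis.
- *That resentment will follow.* This is possible, but nothing in the protocol shows it.
- *That the text was carried over from the door-to-door cluster-randomised trial in section 1.4.* The resemblance is plain, and another tool in the appendix is labelled as coming from 3ie work, but the origin of this script is not stated. The point does not need it.

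**Conclusion.** The point holds in a limited form. The framing sentence in item 6 and the control-zone wording in prompt V contradict sections 1.5 and 4.2, Table 1 and Appendix 1. The full-coverage statement in section 4.1 adds to the conflict for the community-led model. The flaw is one sentence and one prompt in one tool. It may distort the mapping and transect-walk contribution to objective 3, and it gives a key partner a false description of the study. That makes it more than clerical, and it should be corrected before the guide is used.

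The cohorts, the sample size, the primary outcome and the statistical analysis are not affected. The other qualitative guides do not share this error; the mismatched community-led introduction is a separate, smaller fault. The conclusion assumes that the guide is read as written. The number of mapping groups is unknown, so the count of 40 to 60 people is illustrative.

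**What to change.** - **Item 6:** replace the home-delivery sentence with a short description of the distribution models operating in that community. Not every model need appear, since section 4.1 says workplaces may lie outside the five communities.
- **Prompt V:** delete it. If coverage does differ by zone, reword it to ask about that without any mention of a control.
- **Prompts I to IV:** keep them, asked once. Repeating them for every model would mean up to 4 × 5 = 20 prompts. The exercise lasts 45 minutes, of which at least 15 go to building the map, so at most 30 ÷ 20 = 1.5 minutes would be left for each. Prompt IV concerns the clinic and does not suit repetition.
- **IDI (community led models):** change the introduction to shop or kantemba distribution, or withdraw the guide as a near-duplicate of IDI for community led models.

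The cost is a wording change to two guides and a minor notification to the ethics committees. No extra sessions or staff are needed.
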